Trial design and methods:	
Investigation of safety and efficacy includes dose finding and safety of the final selected dose. The initial first cohort will enable identification of a dose to be further studied in a second cohort. This will allow further accrual of safety and efficacy data at the final selected dose.
 
The first cohort will include a treatment group (rtPA + standard of care (SOC)) and a group of matched historical controls that received standard of care alone.
 
The first group of 12 eligible patients will receive nebulised rtPA for 14 days in addition to SOC. Each group will comprise six patients receiving invasive mechanical ventilation (IMV) for moderate to severe ARDS, and six patients with mild ARDS requiring non-invasive ventilation (NIV) or standard oxygen therapy. NIV includes continuous positive airway pressure (CPAP) OR high flow oxygen
 
The primary efficacy assessment will be the change in arterial oxygen saturation levels, specifically arterial hypoxemia using the arterial oxygen to inhaled oxygen ratio (<math>\text{PaO}_2/\text{FiO}_2</math> or <math>\text{SaO}_2/\text{FiO}_2</math>) daily during treatment, at the end of treatment and at 5 days post end of treatment. Primary safety assessments will include monitoring for bleeding events and plasma fibrinogen levels. Patients will be followed up until day 28, discharge from hospital or death - whichever occurs first.
 
These 12 patients will be compared against 24 matched historical controls who received SOC alone. A DMC will be set-up to review emergent safety data during the trial and review and advise on the final study results progression from a pilot study to a statistically powered randomised control trial (RCT) based on the safety and efficacy data that is collected.
 
The second cohort will include a treatment group only. 30 patients will be recruited, which will include a minimum of 10 patients receiving IMV and 10 patients receiving NIV or standard oxygen therapy.

Trial duration per participant:	Informed consent to day 28, discharge or death whichever occurs first.
Estimated total trial duration:	12 months
Planned trial sites:	
Multi site:
 
Royal Free Hospital (Royal Free London NHS Foundation Trust)
 
Barnet Hospital (Royal Free London NHS Foundation Trust)

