## 2.5 Dosing schedule of rtPA for cohort 2 – rationale

During the first surge 9 patients were recruited to the pilot study, with 6 patients receiving IMV and 3 patients receiving non-invasive oxygen support. When the first surge died out, recruitment was not feasible and following discussion with DMC and TMG cohort 1 was closed for further recruitment and historical controls were recruited for evaluation of efficacy to enable a sample size calculation for a larger phase 3 study.

None of the bleeding events were considered related to the tPA. See preliminary safety data for cohort 1 in section 2.7. Final analysis of data is awaited; preliminary review of data is described here.

Preliminary data from the 9 patients from cohort 1 indicated a potential increase in arterial oxygen saturation levels, and importantly no evidence of consumption of fibrinogen nor a decrease in plasminogen levels was observed unlike the changes associated with intravenous administration.

Protocol v8.0 has been prepared at the start of the second UK surge. 30 patients will be recruited to this second cohort, with a minimum recruitment of 10 IMV patients and minimum of 10 patients receiving non-invasive ventilation. Early initiation of treatment appears to more effective, and this may be related either to lower fibrin burden or higher amount of plasminogen from the plasma exudate the substrate for rtPA. In the NIV and standard oxygen therapy group, a loading dose of 20 mg three times a day for 2 days followed by 20 mg twice a day is reasonable as intermittent fibrinolysis is effective. The loading dose potentially can help overcome the accumulation of PAI-1 early in the disease process, and is strong inhibitor of fibrinolysis.

The effect on arterial oxygen saturation levels appears to be less in IMV patients and drug losses can be expected because of the dead space created by the ventilator circuit. To account for this, we propose 20 mg every 8 hrs in patients receiving IMV.

Although the pilot study has used nebulisation every 6hrs, it is very reasonable to decrease the frequency to either twice a day for the non-invasive oxygen support group, or three times a day for the IMV group. The less frequent administration should make it easier for delivery teams.

The maximum duration of treatment will continue to be 14 days with a provision for early termination as described in section 7.3.3.

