The potential for pulmonary haemorrhage has been carefully considered during the study design. This risk is probably related to the generation of plasmin in the alveoli, responsible for the fibrinolysis. To date no bleeding has been seen in anecdotal reports using 1 to 2mg/Kg of nebulised rtPA per day, over 3 - 14 days in patients with plastic bronchitis. Plasmin generation, in addition to the amount of rtPA inhaled, is also related to the availability of plasminogen in the alveoli, which is limited by the amount that can cross the alveolar capillary barrier. Indeed this limited availability has the potential to result in therapeutic failure. The other factor that may contribute to the bleeding is the use of therapeutic anticoagulation. Concurrent therapeutic anticoagulation is common with the use of rtPA as it prevents recurrence of thrombosis. There is emerging evidence that these patients have pulmonary thrombin at the segmental and sub segmental, and importantly they appear to a very strong prothrombotic tendency. It is important to note that the bleeding risk in the literature typically includes the concurrent use of anticoagulants. A strong prothrombotic tendency can result in relative resistance to the action of anticoagulants. Indeed patients presenting with elevated troponin in our organisation have been noted to have atypical coronary thrombosis with regards extent and clot burden .

We hypothesise that this risk will be much reduced if administered by inhalation. This is because relatively little of the drug is expected to cross the alveolar-capillary interface and enter the bloodstream. The doses being used in this study are lower than that used in studies for myocardial infarction and stroke and similar to that used in venous thrombosis. Additionally, as the absorption rate is slow, the rapid inactivation of rtPA in the circulation will prevent accumulation to the level normally associated with bleeding. The background risk of pulmonary bleeding in COVID-19 pneumonia is low, with this symptom reported in only 5% of cases (Huang et al. 2020). The bleeding risk is accurately predicted from the plasma fibrinogen level which provides a measure of the rtPA absorbed. This will be monitored and if plasma fibrinogen levels fall to <1.0 g/L, the further dosing of rtPA in that patient will be stopped. Replacement therapy, either in the form of fibrinogen concentrate or cryoprecipitate will be administered to return fibrinogen to >1.0 g/L.

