## 4 Trial design

### 4.1 Overall design

This is a phase II, open label, single centre, uncontrolled, repeated dose, pilot trial of nebulised rtPA in patients with COVID-19 ARDS.

The study will recruit patients requiring either IMV or non-invasive oxygen support. Eligible patients (or if patients lack capacity, their legal representative) will be provided with an information sheet and informed consent will be sought (see section 6.3). Eligibility will be assessed via routine clinical assessments, which may have been done prior to consent. The only exceptions are a pregnancy test (blood or urine), and possibly any assessments listed in section 7.1 that were not done as per routine care. These must be done following consent, and all screening assessments must have been done during the 24-hour period before dosing with rtPA.

The study will run two cohorts sequentially. In cohort 1, 9 consented patients received nebulised rtPA in addition to SOC. 6 patients were receiving IMV and 3 were receiving non invasive support with NIV or CPAP or high flow oxygen or standard oxygen therapy. As an observational arm, matched historical controls who received standard of care were also recruited at a ratio of 2 controls to every 1 treatment arm patient, resulting in 18 historical controls. Originally, the study aimed to recruit 12 patients with 6 on each ventilation type (IMV and non-invasive oxygen support). This would have resulted in 24 historical controls. After the first wave of COVID-19 cases decreased in August 2020 in the UK it became difficult to continue recruitment, so recruitment closed for cohort 1.

With a second surge underway in early 2021, cohort 2 will aim to recruit more patients during this period to provide more data on the safety of rtPA. Based on the analysis of cohort 1, fewer timepoints will be collected (see sections 7.1.2 and 7.5.2), which will allow for more rapid recruitment while at the same time not compromising safety monitoring. A more flexible dosing regimen for rtPA will be utilised which is described in section 7.3.2. 30 patients will be recruited in total, with an aim to recruit a minimum of 10 IMV patients and 10 patients on non-invasive oxygen support.

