Although there is extensive experience with the use of nebulised rtPA in the context of the underlying inflammation, safety measures been included. A gap of 24hrs will be maintained between first and second patient. At 24hrs if patient 1 has no evidence of major pulmonary bleeding suggesting exaggerated alveolar fibrinolysis and no evidence of fibrinogen reduction of more than 50%, suggestive of systemic absorption a second patient will be dosed. Both patients will be evaluated for 72 hrs. If no major bleeding is noticed and fibrinogen levels have not decreased more than 50% in either patient (in line with stopping criteria – section 7.10), and no other stopping criteria have been met, then the rest of the cohort can be recruited after the review of the safety data by the trial management group comprised of the investigators. If there are any concerns with the data this will be referred to the DMC for review. If the safety profile is acceptable, dosing of the third and subsequent patients in the rtPA group will resume with no required interval between patients.

Efficacy will be described as a change in  $\text{PaO}_2/\text{FiO}_2$  (or  $\text{SaO}_2/\text{FiO}_2$ ) ratio assessed daily, end of treatment and 5 days post treatment in relation to baseline. A Data Monitoring Committee (DMC) will be set-up to review safety data within the trial along with the final study results and advise on progressing from a pilot study to a randomised control trial based on the safety and efficacy data that is collected. The DMC will receive weekly reports on bleeding complications, both major and minor along with fibrinogen levels. If at any time a patient has major pulmonary bleeding, further dosing of patients will be stopped and an adhoc DMC review will be arranged before resuming dosing (see section 12.2 Data Monitoring Committee).

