## 7.5 Visit schedule and assessments post initiation of treatment

### 7.5.1 Cohort 1 and 2

Any assessments that are done as per routine care do not need to be repeated.

- Documentation of respiratory status: Respiratory status of patients is monitored hourly and data points will be extracted for every four hours where available until 5 days after the last dose for cohort 1, but one data point per day is required as a minimum. For cohort 2 data will be extracted once a day coinciding with the worst PF ratio. As PF ratio is the primary endpoint, in addition to the worst PF ratio over the preceding 24 hrs up to a maximum of 6 data points spread across 24 hrs that represents patients clinical status will be extracted. Similar to cohort 1 respiratory data will be collected until 5 days after the last dose. After this period, respiratory status is to be documented weekly (+/- 1 day) until discharge, death, or 28 days whichever occurs first. The time of measurement should be documented.
- The variables include:
  - Details of oxygen and respiratory support including the type of device, FiO2 Respiratory rate
  - PaO2
  - For IMV patients, details of ventilation including but not exclusively the below
    - Tidal volume (in mL)
    - Full sedation or not – not for cohort 2
    - Paralysis or not – not for cohort 2.
    - Patient position – not for cohort 2
    - Peak inspiratory pressure (collected for computing compliance)
    - PEEP (collected for computing compliance)
  - For non-invasive oxygen support patients:
    - National Early Warning Score (NEWS 2) – not for cohort 2
    - Oxygen flow rate
    - SpO2
  - For CPAP patients
    - Positive end expiry pressure (PEEP)

The following tests are to be done at a minimum once a day until 5 days after the last dose (day 7 for SOC patients) in cohort 1, a minimum every other day in cohort 2, and then as required until day 28, discharge or death whichever occurs first.

- Local blood testing as per section 7.6.2

The following tests will be done once at 48 h (+/- 24 h) and 96 h (+/- 24h) after start of treatment and then twice weekly while on treatment until 5 days after stopping treatment. After this period, testing should be weekly (+/- 1 day) until day 28, discharge or death whichever occurs first. Twice weekly testing should be evenly spaced across weekdays if possible.

- Research blood sampling as per section 7.6.2

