## 7.10 Stopping rules

The trial may be stopped before completion for the following reasons:

- On the recommendation of the sponsor and CI
- A major pulmonary bleeding that is symptomatic or fatal that occurs between start of treatment and 30 hours after the last dose.
- Cohort 1 - A 50% or greater reduction of fibrinogen at 72 hrs (from baseline value at screening) in either of the first 2 patients after dosing. If we see a 50% or greater drop in fibrinogen in a patient, it would only be a particular safety concern in that patient if the fibrinogen were to go below 1.5 g/L (hence why this level is stated as a reason to stop dosing in an individual patient). However, if we do see a 50% drop in fibrinogen from baseline values in either of the first 2 patients it might suggest that the dose is too high overall with secondary systemic absorption. As such stopping the trial will provide us the opportunity to discuss within the TMG and IDMC to make a decision on the dose going forward. A substantial amendment would be made to the MHRA and REC.
- Any fatal bleeding that occurs between start of treatment and 30 hours after the last dose.
- Symptomatic bleeding in a critical area or organ, such as intracranial, intraspinal, pericardial, pulmonary or intramuscular with compartment syndrome, that occurs between start of treatment and 30 hours after the last dose.

Further enrolment into the study will be put on hold in the event of any of the stopping rules and a substantial amendment will be submitted to temporarily halt the trial. Whenever the study is stopped in addition to a review of the data by the trial management group consisting of the investigators, the DMC will also be convened for review of the data to assess the risk benefit of progressing the pilot study. If, following an internal safety review by the DMC, the Sponsor deems it appropriate to restart the trial; this can only be done following approval by the MHRA and REC and along with any local approvals required.

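### Cohort 2 is presented as further data at the dose selected in cohort 1, but cohort 1 did not use its schedules, fibrinogen sampling is thinned on cohort 1 results, and it is unclear which first-patient checks still apply

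*Protocol*

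**What the plan says.** Section 1 of the protocol sets out a sequence: "The initial first cohort will enable identification of a dose to be further studied in a second cohort", and then "This will allow further accrual of safety and efficacy data at the final selected dose".

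The schedules are in Section 7.3. Cohort 1 (7.3.1) is 10 mg every 6 h, at most 56 doses. Cohort 2 (7.3.2) is 20 mg every 8 h for IMV patients, 42 doses. For non-invasive patients it is 20 mg every 8 h for two days and then every 12 h, 30 doses. Section 2.5 explains the change from preliminary results in nine patients, expected losses in the ventilator circuit, inhibitor levels early in disease and ease of delivery. For example, "we propose 20 mg every 8 hrs in patients receiving IMV".

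On monitoring, Section 4.1 bases the reduced timepoints on the cohort 1 analysis and describes the reduction as one "which will allow for more rapid recruitment while at the same time not compromising safety monitoring". Section 7.5.1 sets local blood tests, which include fibrinogen, at a daily minimum in cohort 1 and at "a minimum every other day in cohort 2"; Appendix 1 agrees. Section 2.6 gives fibrinogen a central role: "The bleeding risk is accurately predicted from the plasma fibrinogen level which provides a measure of the rtPA absorbed". A fall below 1.0 g/L, during treatment or within 48 h after the last dose, is a primary safety endpoint (10.1.2).

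On the first patients, Section 4.1 says "A gap of 24hrs will be maintained between first and second patient" and names no cohort. Section 12.1 gives the management group's 24 h and 72 h checks, also without a cohort. Section 12.2 puts the referral from those reviews under its cohort 1 heading, and Section 7.10 opens its rule with "Cohort 1 - A 50% or greater reduction of fibrinogen at 72 hrs".

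**The concern.** The Section 1 wording tells a reader that cohort 2 adds patients to a dose on which there is already trial experience. If the schedules are new, the first cohort 2 patients are the trial's first exposure to them, and the cohort 1 results bear on them only indirectly.

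This matters most for fibrinogen. The protocol treats it as the marker of absorbed drug, the trigger for stopping an individual patient, and a primary safety endpoint. Results at a lower single dose are being used to support a longer minimum gap between fibrinogen tests at a higher one. Section 7.10 explains that a 50% fall in either of the first two patients might mean the dose is too high, yet that rule is confined to the cohort with the smaller single dose. Site staff also cannot tell from the text whether the first cohort 2 patients are to be staggered and reviewed as in cohort 1.

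**Working it through.** **1. Reproduce the stated dose counts (7.3.1, 7.3.2).** Cohort 1: 14 × 4 = 56. Cohort 2 IMV: 14 × 3 = 42. Cohort 2 non-invasive: 2 × 3 + 12 × 2 = 30. All three agree with the protocol.

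**2. Compare exposure with cohort 1.**

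| | Cohort 1 | Cohort 2 IMV | Cohort 2 non-invasive |
|---|---|---|---|
| Single dose | 10 mg | 20 mg (×2) | 20 mg (×2) |
| Daily dose, days 1-2 | 40 mg | 60 mg (×1.5) | 60 mg (×1.5) |
| Daily dose, days 3-14 | 40 mg | 60 mg (×1.5) | 40 mg (×1.0) |
| Course maximum | 56 × 10 = 560 mg | 42 × 20 = 840 mg (×1.5) | 30 × 20 = 600 mg (×1.07) |

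No cohort 1 schedule contains a 20 mg dose or a 60 mg day.

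**3. Drug given between two minimum-frequency fibrinogen tests (7.5.1, Appendix 1).**
- Cohort 1, 24 h: 4 × 10 = 40 mg.
- Cohort 2 IMV, and non-invasive on days 1-2, 48 h: 6 × 20 = 120 mg, a ratio of 3.
- Cohort 2 non-invasive from day 3, 48 h: 4 × 20 = 80 mg, a ratio of 2.

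A factor of 2 comes from the longer interval. The rest, ×1.5 or ×1.0, is the daily dose.

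**4. What the cohort 1 fibrinogen result can exclude.** Section 2.7.3 reports no patient below 1.5 g/L among the nine treated. With 0 of n, the one-sided 95% upper bound is 1 − 0.05^(1/n). For n = 9 this is 28.3%; for the 6 IMV patients, 39.3%; for the 3 non-invasive patients, 63.2%. These bounds are for the cohort 1 schedule only.

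**5. Chance that a short fall lies wholly between samples.** The documents give no duration for a fall, so I assume a range, with onset uniform over the sampling interval. The chance of missing a fall of duration d with interval L is max(0, 1 − d/L).

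| Assumed duration | L = 24 h | L = 48 h |
|---|---|---|
| 12 h | 50% | 75% |
| 24 h | 0% | 50% |
| 36 h | 0% | 25% |

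These apply if only the minimum is sampled.

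**6. Checks on the first patients, side by side.**
- 50% fibrinogen fall in either of the first two patients: cohort 1 only (7.10).
- 24 h gap and 72 h evaluation: no cohort named (4.1), though the text follows a paragraph giving the cohort 1 dose.
- 24 h and 72 h management-group checks: no cohort named (12.1).
- Referral from those reviews to the Data Monitoring Committee (DMC): under cohort 1 (12.2).
- Weekly DMC reports: no cohort named in 4.1, under cohort 1 in 12.2.
- Individual fibrinogen level for stopping dosing: 1.0 g/L in 7.3.3 and 7.4, but 7.10 refers to 1.5 g/L as the stated level.

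**The case against.** The change of schedule is not hidden: Section 2.5 states it, gives reasons and calls the cohort 1 data preliminary. Section 10.6 analyses the cohorts separately and treats all results as hypothesis generating. Cohort 2 keeps the bleeding stopping rules (7.10), the individual fibrinogen stop (7.3.3, 7.4), daily review of bleeding during treatment (7.5.1), management-group and DMC meetings after every ten patients, and a dosing halt with ad hoc DMC review if a stopping criterion is met (12.1, 12.2). All of this stands, and it limits the point to the Section 1 wording, the monitoring claim and the unlabelled checks.

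A reader might infer more than the documents support, in four ways:

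- **That the staggered start and early reviews have been removed for cohort 2.** Only the 50% fibrinogen rule is expressly limited to cohort 1. The others are ambiguous.
- **That cohort 1 says nothing about the new schedules.** Stable fibrinogen, and plasminogen and antiplasmin within normal limits, at a lower single dose by the same route (2.7.3, 2.7.4) are limited but relevant evidence. Sections 2.4 and 2.6 also cite outside reports of nebulised use.
- **That the cohort 2 fibrinogen endpoint is bound to look cleaner.** Every other day is a minimum and routine care may sample more often. The higher dose and the lower entry level (1.5 g/L in 6.1.4, against 2.0 g/L in 6.1.2) could push observed events up.
- **That 60 mg a day matches the intravenous range of 0.9 to 1.2 mg/kg in Section 2.6.** That range is given over 1 to 2 h. A nebulised daily total in three divided doses is not comparable.

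**Conclusion.** The point holds in a limited form. The Section 1 description is wrong on the protocol's own schedules: cohort 2 doubles the single dose, and the daily dose is 1.5 times that of cohort 1 except for non-invasive patients from day 3, where it is equal. The statement that monitoring is not compromised has no support specific to these schedules, since the drug given between minimum fibrinogen tests is two to three times the cohort 1 amount. No events in nine patients is compatible with a true rate of up to 28% even on the cohort 1 schedule.

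The dose ratios follow directly from the protocol. The missed-fall figures rest on assumed durations, uniform onset and minimum-frequency sampling, so they show how detection could differ between cohorts and do not predict what will be observed. Which first-patient checks apply to cohort 2 is unresolved in the text. I take no view on which dose, threshold or clinical rule is right.

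**What to change.** 1. **Section 1.** State that cohort 2 uses schedules not given in cohort 1, and that the cohort 1 safety data are indirect and limited evidence for them.
2. **Sections 4.1, 7.10, 12.1 and 12.2.** Reconcile these so that each first-patient check names the cohort it applies to. In the same amendment, reconcile the individual fibrinogen level in 7.3.3 and 7.4 (1.0 g/L) with that in 7.10 (1.5 g/L).
3. **Primary fibrinogen endpoint, cohort 2.** Extract every routinely available local fibrinogen result from the first dose to 48 h after the last, and report the actual sampling interval. The separate cohort 2 analysis plan promised in 10.6 is the natural place. It should say that the endpoint is not directly comparable between cohorts where sampling differs.
4. **Section 4.1.** Either justify the every-other-day minimum for the new schedules or remove the statement that safety monitoring is not compromised.

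The cost is a wording amendment and slightly more data entry. Section 7.6.2 places these tests within clinical care, so item 3 asks for extraction and not for additional blood samples.

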### 7.3.3 Treatment discontinuation

Treatment may be stopped at any point in a patient if any of the following rules are met:

- If plasma fibrinogen levels fall to <1.0 g/L, the further dosing of rtPA in the patient will be stopped (see section 7.4).
- Patient maintains saturation on room air that is either normal or normal for them for 48 hours as assessed by the investigator
- A trial stopping rule has been met (see section 7.10)

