### 7.3.4 Re-treatment with rtPA after treatment discontinuation due to improvement in patient saturation (as described above)

If there is a recurrence of COVID-19 ARDS related symptoms or a worsening of PaO2/FiO2 ratio, which the investigator considers could be related to treatment discontinuation, treatment can be restarted. The decision to re-treat will be made within 5 days (120 hrs) from the last dose of treatment. Treatment may not be restarted more than once.

The rationale for restarting of treatment must be documented in the notes, along with the absence of toxicity. The patients monitoring will done according to main treatment phase.

### 7.3.5 Re-treatment of patients previously consented and treated on the trial – Cohort 1

For patients that have already been treated under the previous 3 day dosing schedule, if they remain eligible for the trial, they will be offered the option to continue treatment as above – the maximum number of days of extra treatment for these patients will be 11 days. Patients (or their legal representatives) must give consent to this re-treatment.

The total duration of trial participation for these patients may exceed 28 days (to approximately 5-6 weeks) to allow us to extend treatment to the maximum 14 days and to allow us to collect 5 days of post treatment data. We will inform the patient or their legal representative of this possibility and this will be documented in the patient information sheet.

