## 7.11 Definition of End of Trial

The end of trial is the date of discharge, death, or day 28 of the last patient whichever is sooner.

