## 8.2 Recording adverse events

All adverse events will be recorded in the medical records in the first instance. Non-serious AEs will not be collected in the CRFs for this trial, apart from the adverse events of special interest (AESI) listed below:

- Bleeding events

In addition, any Serious Adverse Events (SAEs) assessed as likely to be related to IMP administration will be collected. See section 8.4 for further details on recording and reporting of Serious Adverse Reactions (SARs). These AESIs and Serious Adverse Reactions (SARs) will be recorded with clinical symptoms and accompanied with a simple, brief description of the event, including dates as appropriate, until the participant completes the trial.

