### 10.1.2 Safety

1. Incidence and severity of major bleeding events directly attributable to the study drug
2. Decrease in fibrinogen levels to  $< 1.0 \text{ gm/L}$  during treatment period and 48 hrs after the last dose of treatment
3. Number and nature of serious adverse events causally related to the treatment

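### Follow-up ends at discharge, but the bleeding, fibrinogen and adverse-event windows run on time since the last dose, and no procedure finds events in a patient who has already gone home

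*Protocol*

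**What the plan says.** **End of observation.** Protocol section 1 gives the trial duration per participant as "Informed consent to day 28, discharge or death whichever occurs first", and the design summary in the same section says "Patients will be followed up until day 28, discharge from hospital or death - whichever occurs first". Section 7.11 uses the same three limits for the trial: "The end of trial is the date of discharge, death, or day 28 of the last patient whichever is sooner". Under section 8.2, recording of bleeding events of special interest and serious adverse reactions (SARs) stops once the participant completes the trial. No telephone, clinic or record follow-up of treated patients after discharge is described.

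**Windows timed from the last dose.**
- Section 7.10, stopping rules: "Any fatal bleeding that occurs between start of treatment and 30 hours after the last dose". The other bleeding rules carry the same 30-hour limit.
- Section 10.1.2, primary fibrinogen endpoint: "during treatment period and 48 hrs after the last dose of treatment".
- Section 7.5.1: adverse-event and bleeding review daily until 5 days after the last dose.
- Section 7.3.4, re-treatment after stopping for improvement: "The decision to re-treat will be made within 5 days (120 hrs) from the last dose of treatment".

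**How treatment can end early.** One of three listed grounds in section 7.3.3 is "Patient maintains saturation on room air that is either normal or normal for them for 48 hours as assessed by the investigator". The section says treatment may be stopped, not that it must be.

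**Text that points the other way.** Section 8.4 records SARs from the start of treatment to the end of the study. Section 7.5.1 and Appendix 1 attach discharge only to the phase after the 5-day post-dose period.

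**The concern.** Safety is a primary objective, and section 4.1 gives more safety data as the purpose of cohort 2. The Data Monitoring Committee (DMC) uses those data to advise on a randomised trial (section 12.2). The windows tell the reader how long after dosing a patient is regarded as at risk, but observation is tied to a different clock, namely being in hospital.

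A patient whose treatment stops after 48 hours of good saturation on room air no longer needs oxygen, so discharge soon afterwards is plausible. If that patient bleeds at home or is readmitted inside a window, nothing in the plan leads the team to learn of it. Counts of bleeds and related serious events could then be too low, mainly because of patients who responded and left early, while the percentages would appear to rest on everyone treated. A bleed that meets section 7.10 could also go unnoticed when it should prompt a hold on enrolment.

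**Working it through.** The plan has no figure of its own on this point to reproduce. Both sample sizes are stated to be non-statistical (section 10.4.1).

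**Step 1. Which limit can cut the windows?** Inputs are the dosing tables in sections 7.3.1 and 7.3.2, for an uninterrupted full course. Day 28 ends at 28 × 24 = 672 h.

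| Schedule | Doses | Last dose (h) | Plus 120 h |
|---|---|---|---|
| Cohort 1 | 14 × 4 = 56 | 55 × 6 = 330 | 450 |
| Cohort 2, IMV | 14 × 3 = 42 | 41 × 8 = 328 | 448 |
| Cohort 2, non-invasive | 2 × 3 + 12 × 2 = 30 | 48 + 23 × 12 = 324 | 444 |

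The dose counts match the protocol. The longest window closes at 444 to 450 h, well before 672 h. Apart from death, discharge is therefore the limit that can cut a window short.

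**Step 2. How much of each window is seen?** Share observed = min(hours from last dose to discharge ÷ window length, 1). The discharge times are assumptions, since the documents give none.

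| Discharge after last dose | 30 h window | 48 h window | 120 h window |
|---|---|---|---|
| 12 h | 40% | 25% | 10% |
| 24 h | 80% | 50% | 20% |
| 48 h | 100% | 100% | 40% |
| 72 h | 100% | 100% | 60% |
| 120 h | 100% | 100% | 100% |

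The 5-day review is the most exposed. The 30 h window is affected only if discharge comes within 30 h.

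**Step 3. What could this do to the information in cohort 2?** Suppose a share of the 30 patients is discharged inside a window and, as a simplification, count only fully observed patients (n, rounded down). After zero events the one-sided 95% upper bound is 1 − 0.05^(1/n). The chance of seeing at least one event at an assumed true rate of 5% is 1 − 0.95^n.

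| Share discharged early (assumed) | n | Upper bound | Chance of at least one event |
|---|---|---|---|
| 0% | 30 | 9.5% | 78.5% |
| 10% | 27 | 10.5% | 75.0% |
| 25% | 22 | 12.7% | 67.6% |
| 50% | 15 | 18.1% | 53.7% |

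The group most likely to be exposed is the non-invasive one: at least 10 and at most 30 − 10 = 20 of the 30 patients. That is the size of the group, not the number expected to leave early.

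**Step 4. Do the sections agree?** Sections 1, 7.11 and 8.2 stop at discharge or at completion. Section 8.4 runs to the end of the study. On one reading this is set by the last patient (7.11), so a SAR in an earlier discharged patient remains recordable. However, 7.5.1 uses end-of-study data for what is collected at a participant's own discharge, so the term is ambiguous. Section 7.5.1 and Appendix 1 can be read as requiring all 5 days whatever the discharge date, but give no means of doing so for a patient at home.

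**The case against.** The case for the plan has real weight.

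- **A reader might infer that nothing is collected after discharge.** Section 8.4 does not support that: a SAR reported later may still be recordable. It sets a recording period, though, not a way of finding events, and it does not cover non-serious bleeds.
- **A reader might infer that the stopping rules cannot operate after discharge.** Section 7.10 defines its bleeding triggers by hours since the last dose and never says that they lapse. A bleed the team hears of can be acted on. The gap is in hearing of it.
- **A reader might infer that the room-air rule selects patients for discharge, so the windows are cut short.** The rule is permissive, and no discharge criteria or times appear. The 48-hour mark may also fall between 12-hourly doses, so up to about 12 hours of the window may already have passed in hospital. The windows can be cut short; that they are is not shown.
- **Hours lost are not information lost.** Cohort 2 fibrinogen is measured at least every other day, and the protocol gives a circulating half-life of minutes (section 2.6), so risk need not be even across a window. The percentages above describe coverage, not bias.
- **Cohort 1 captured late events.** Six of seven bleeds were recorded after the 30-hour exposure period (section 2.7), and fibrinogen to 48 hours was reported (2.7.3). These data are not split by response, and six of the nine patients were on IMV, so they do not settle the matter for cohort 2.
- **Analysis.** The primary bleeding endpoint has no 30-hour limit, analyses are descriptive, and cohort 2 is to have its own SAP (10.6), so its denominators are not known here.

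What remains is the absence of any planned ascertainment after discharge, and the conflict between sections.

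**Conclusion.** The concern holds as a gap in ascertainment and an inconsistency in the text. If a patient is discharged before a post-dose window closes, no procedure finds a later bleed, related serious event or death. Such events can be missed, and the most exposed patients are responders discharged early. Any error in the bleeding and related serious-event counts from this source would be downward.

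The size cannot be stated. It depends on the share discharged inside each window and on when in the window risk falls, neither of which the documents give. Under the assumed shares of 10% to 50%, the number of cohort 2 patients fully observed falls from 30 to between 27 and 15, and the zero-event bound rises from 9.5% to between 10.5% and 18.1%. This is worth correcting because it is cheap and safety is a primary objective. It is not evidence that reported rates are biased.

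**What to change.** 1. Reconcile sections 1, 7.11 and 8.2 with 7.5.1, 7.10, 8.4, 10.1.2 and Appendix 1, so that bleeding, related serious events, readmission and vital status are ascertained regardless of discharge.
2. For patients discharged before 5 days after the last dose: telephone soon after the 30-hour window closes, make a second contact at the end of the 5-day window, and check the Trust record at day 28. Section 6.4 confirms that the study team can see records at both hospitals. A day-28 contact alone would come too late for a rule with a 30-hour limit.
3. Report any qualifying bleed found this way to the DMC under section 7.10.
4. Require no blood test after discharge. Neither calls nor a record check can be relied on to recover a missing fibrinogen value. Instead, report how many patients had each window fully observed and how many had a fibrinogen value within 48 hours after the last dose, and use those numbers as denominators alongside all treated patients. For cohort 2 this belongs in its separate SAP.

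The cost is amendment wording, a line in the information sheet, and a few calls and one record check per discharged patient (at most about 30 in cohort 2). The end of trial may move to day 28 of the last patient.
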